9.2. Statistical Method

9.2.1. Computation of incidence rate

The incidence rate of first event (IR, number of first episodes per 1000 person-years) will be calculated by dividing the number of subjects reporting at least one episode of event during the follow-up period by the total person-year at risk.

The person-time at risk for an event of interest (e.g. AFI due to LCD) will be calculated as the duration between the date of enrolment and the end of the at-risk period or the earliest of the following:

- Onset date of event of interest (e.g. first episode of AFI due to LCD)
- Date of last contact
- Date of death.

9.2.2. The method for estimating the CIs for incidence rate not accounting for clustered data

To estimate the confidence interval of the incidence rate, the exact Poisson confidence interval will be used [Clopper, 1934].

If n is the number of subjects presenting a given characteristic among these Ny subjects per year, the true incidence rate per 1000 person-years can be estimated by $(n/Ny)*1000$. Its exact $(1-\alpha)\%$ confidence interval is obtained from:

$CINV(\alpha/2, 2*n)/2/Ny*1000$ as the lower boundary

and

$CINV((1-\alpha)/2, 2*(n+1))/2/Ny*1000$ as the upper boundary.

where $CINV$ (*probability, degrees of freedom*) returns the inverse of the chi-squared probability distribution and α is the type I error rate, which will be 0.05 for calculating a 95% CI.

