9.2. Sample size considerations

A **maximum of 2,000** subjects will be enrolled for a 2-year follow-up period. Assuming a drop-out rate of 10% the first year and a drop-out rate of 20% the second year, the final analysis will be done on approximately **3300** person-years overall.

In order to evaluate the precision with a sample size of **3,000** subjects, the 95% confidence interval (CI) (Poisson exact distribution and normal approximation of the Poisson distribution accounting for a design effect) for a range of expected incidences rates of AFI due to LCD were computed. The 95% CI for a range of expected incidences rates for DENV specific LCD were also presented (see [Table 17](#)).

(Amended 01 March 2017)

Estimating design effect and precision

The normal approximation of the Poisson distribution was used for calculating 95% CI for this cluster design. The variance was adjusted for a design effect of 2.6 to account for the between-cluster variability. The design effect measures the increase in the standard error of the estimate due to the sampling design used and is given by: $D = 1 + (b - 1) \rho$, where ρ is the rate of homogeneity (a measure of variability and equivalent to the “intra-cluster correlation”) and b is the average number of subjects sampled per household. Here we assumed b to be 5. Although, in theory ρ can have a value up to 1, in practice values higher than 0.4 are uncommon [Bennett, 1991]. We used a conservative estimate of 0.4 for this study. The design effect is then estimated to 2.6.

Table 17 95% CI with design effect of 2.6

	Number of cases	Number of person-years	Incidence of LCD (per 100 person-years)	95% CI Poisson exact		95% CI Normal approx with design effect of 2.6	
				LL	UL	LL	UL
Overall	10	3300	0.30	[0.15 ; 0.56]		[0.00 ; 0.61]	
	20	3300	0.61	[0.37 ; 0.94]		[0.18 ; 1.03]	
	30	3300	0.91	[0.61 ; 1.30]		[0.38 ; 1.43]	
	40	3300	1.21	[0.87 ; 1.65]		[0.61 ; 1.82]	
	50	3300	1.52	[1.12 ; 2.00]		[0.84 ; 2.19]	
	60	3300	1.82	[1.39 ; 2.34]		[1.08 ; 2.56]	
DENV specific	4	3300	0.12	[0.03 ; 0.31]		[0.00 ; 0.31]	
	8	3300	0.24	[0.10 ; 0.48]		[0.00 ; 0.51]	
	12	3300	0.36	[0.19 ; 0.64]		[0.03 ; 0.70]	
	16	3300	0.48	[0.28 ; 0.79]		[0.10 ; 0.87]	

(Amended 01 March 2017)

CI: confidence interval**DENV:** dengue virus**LCD:** laboratory Confirmed Dengue**LL:** lower limit;**UL:** upper limit

At time of analysis, the design effect of this study will be estimated using the following formula [Bennett, 1991]:

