$$DE = \frac{s^2_{\text{CLUSTER SAMPLE}}}{s^2_{\text{SIMPLE RANDOM SAMPLE}}}$$

With

$$s^2_{\text{CLUSTER SAMPLE}} = (c/\sum x_i)^2 (\sum y_i^2 - 2p \sum x_i y_i + p^2 \sum x_i^2) / [c(c-1)]$$

$$s^2_{\text{SIMPLE RANDOM SAMPLE}} = p(1-p)/n$$

Where, c is the number of clusters, x_i and y_i are the number of person-years and the number of cases, respectively in the i^{th} cluster, n is the total number of person-years and p is the overall proportion $\sum y_i / \sum x_i$.

The intra-cluster correlation ρ may then be estimated as:

$$\rho = (DE - 1) / [(\sum x_i/c) - 1]$$

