5.2. Primary objective

5.2.1. Analysis of primary objective planned in the protocol

The incidence rate of first AFI due to LCD will be calculated along with 95% exact confidence interval. This analysis will be based on the total enrolled set. See section 9.2.1 and section 9.2.2 for details of incident rate and confidence interval calculation respectively.

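### The SAP omits the design-effect estimate promised in Protocol 9.2 and uses an exact Poisson interval that ignores household clustering; with five per household it is too narrow from a rho of about 0.1 upward

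*SAP*

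**What the plan says.** **Protocol 9.2** treats households as clusters. It takes the design effect as D = 1 + (b - 1)rho, where "b is the average number of subjects sampled per household", and sets b to 5. On rho it says: "We used a conservative estimate of 0.4 for this study". For the precision table, "The variance was adjusted for a design effect of 2.6 to account for the between-cluster variability". It then commits: "At time of analysis, the design effect of this study will be estimated using the following formula". The formula that follows is the ratio of a between-cluster variance to a simple-random-sample variance, where x and y "are the number of person-years and the number of cases, respectively in the" i-th cluster.

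**Protocol 9.6** asks for incidence rates with 95% CIs and names no method. **Protocol 9.10** says that changes from the plan will be explained in the final report.

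**SAP 5.2.1**, whose heading says the analysis is the one planned in the protocol, states: "The incidence rate of first AFI due to LCD will be calculated along with 95% exact confidence interval". SAP 5.3.1 does the same for the secondary rates. The method is in SAP 9.2.2, headed "The method for estimating the CIs for incidence rate not accounting for clustered data". The SAP text has no design effect, rho, robust variance or adjusted interval. Section 8, on changes from planned analyses, lists tertiary items only. The table shells are filed elsewhere (SAP 10.2) and could not be checked.

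**The concern.** Protocol 5.1 prefers to enrol every eligible member of a household, and members share exposure to the same mosquitoes. The protocol's own tertiary endpoints look for further dengue cases in the index case's household. If cases cluster in this way, a Poisson interval that treats subjects as independent is too short.

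The primary objective is an incidence rate, and its 95% CI is the only measure of precision attached to it. Protocol 3.1 says the incidence data are to feed sample size calculations for later efficacy trials, so an interval that is too short passes false precision to those trials. SAP section 8 also drops the spatio-temporal clustering analysis. Without a design effect, no analysis in the SAP text would show how far cases cluster, and a reader could not tell whether the interval is sound.

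**Working it through.** **1. The plan's own figures.** Inputs from Protocol 9.2: b = 5, rho = 0.4, 2000 subjects, about 3300 person-years (PY).

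- D = 1 + (5 - 1) × 0.4 = 2.6, as stated.
- With the stated drop-out, 2000 × 0.9 + 2000 × 0.9 × 0.8 = 3240 PY, close to 3300.
- Table 17 uses exact limits chi2(0.025, 2n)/2/PY and chi2(0.975, 2(n + 1))/2/PY, and adjusted limits n/PY ± 1.96 × sqrt(D × n)/PY. For 40 cases these give 0.87 to 1.65 and 0.61 to 1.82 per 100 PY, as printed. All ten rows reproduce to two decimals.
- At D = 2.6 the adjusted interval is 1.47 (10 cases) to 1.56 (60 cases) times as wide as the exact one.

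**2. Coverage of the exact interval under clustering.** Assumptions: beta-binomial household counts, about 2000 subjects, equal household sizes, 40 expected cases, correct upper limit. Coverage was obtained by simulation (6000 runs, 1.65 PY per subject, follow-up ending at the first case) and separately by exact convolution. The last two columns cover the protocol's ratio-estimator variance with limits on the log scale.

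| rho | Exact CI, b = 5: simulation / convolution | Exact CI, b = 3: simulation / convolution | Adjusted CI, b = 5 | Adjusted CI, b = 3 |
|---|---|---|---|---|
| 0.02 | 95.3% / 95.5% | 95.8% / 95.9% | 94.9% | 95.2% |
| 0.05 | 94.4% / 94.3% | 94.9% / 95.3% | 95.2% | 94.8% |
| 0.1 | 91.9% / 92.2% | 94.2% / 94.3% | 94.9% | 95.2% |
| 0.2 | 87.8% / 87.9% | 91.8% / 92.2% | 94.3% | 94.8% |
| 0.4 | 80.5% / 80.2% | 87.4% / 87.9% | 94.7% | 95.1% |

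Over Table 17's overall counts (10 to 60 cases, b = 5), convolution gives exact-CI coverage of 93.3 to 96.1% at rho 0.05, 91.0 to 94.4% at 0.1 and 78.6 to 83.5% at 0.4. The exact interval is slightly conservative and absorbs a small rho. From 0.1 upward it falls short of 95% at every one of these counts.

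**3. What this does to the interval.** At 40 cases in 3300 PY the rate is 12.1 and the exact CI 8.7 to 16.5 per 1000 PY. The adjusted limits are rate × exp(± 1.96 × sqrt(DE/40)):

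- DE 1.2 (rho 0.05): 8.6 to 17.0
- DE 1.4 (rho 0.1): 8.4 to 17.5
- DE 1.8 (rho 0.2): 8.0 to 18.4
- DE 2.6 (rho 0.4): 7.4 to 20.0

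**4. Low counts and unequal households.** With b = 5 and rho 0.4 (4000 runs), coverage of the exact and adjusted intervals was 79.8% and 94.4% at 16 cases, 79.1% and 92.9% at 12, and 81.7% and 89.0% at 8. With household sizes 2 to 8 (mean 5), rho 0.4 and 40 cases it was 76.7% and 94.0%.

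**5. The protocol's rho formula.** It divides DE - 1 by mean person-years per household minus 1, whereas the planning formula uses subjects. With 5 × 1.65 = 8.25 PY per household, (2.6 - 1)/(8.25 - 1) = 0.22, against (2.6 - 1)/(5 - 1) = 0.40. The DE and the interval are not affected.

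**6. The printed upper limit in SAP 9.2.2.** It uses the quantile (1 - alpha)/2 = 0.475 where 1 - alpha/2 = 0.975 is needed. Taken literally, 40 cases give 8.7 to 12.2 per 1000 PY instead of 8.7 to 16.5, and zero cases give an upper limit of 0.20 instead of 1.12. Coverage is about 50% even without clustering. It also contradicts Table 17's exact upper limit of 1.65 per 100 PY.

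**The case against.** Several points on the other side stand:

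- Table 17 prints exact Poisson limits beside the adjusted ones, Protocol 9.6 names no method, and Protocol 9.2 never says the reported CI will be adjusted. The broken commitment is therefore the missing DE estimate; the adjusted interval is a recommendation.
- The SAP 9.2.2 heading is open about the limitation, and Protocol 9.10 leaves room to justify the change in the final report. The lack of a record is a statement about SAP section 8 only.
- Harm is small when rho is small. The 80% figure needs rho 0.4, which at a 2% risk (40/2000) means a case's housemate has about a 41% chance of also being a case (0.02 + 0.4 × 0.98).
- All analyses are descriptive (SAP 6), and the protocol says dengue incidence varies greatly between years, which no household DE captures.
- Adjusted limits lose accuracy at low counts, and Table 17's serotype rows have only 4 to 16 cases.
- Protocol 5.1.1 allows a first stage of at least eight blocks or streets. If that was used, household adjustment may not suffice: with an assumed 8 blocks, household rho 0.1, 40 expected cases and a between-block coefficient of variation of 0.3 or 0.5, adjusted coverage was 91% or 85% (3000 runs).
- The quantile error is a separate defect and may be a typing or conversion slip.

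These points limit the size of the concern. They do not supply the missing estimate, and without it nobody can show that rho was small.

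**Conclusion.** The concern holds. The SAP omits an estimate that the protocol commits to, gives no reason, and leaves the primary rate with an interval that ignores the planned cluster design. The loss is negligible at rho 0.05 or below. With five per household and 40 cases, coverage is about 92% at rho 0.1, 88% at 0.2 and 80% at 0.4; with three per household it is about 94%, 92% and 87 to 88%. These figures assume beta-binomial households of equal size and no block-level clustering, and the realised rho and household size are unknown. Rates themselves do not change and no decision rule depends on them (Protocol 9.9). This should be fixed, but it does not undermine the study.

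**What to change.** - In SAP 5.2.1, 5.3.1 and 9.2.2, estimate and report the DE by the Protocol 9.2 formula with household as the cluster. This alone closes the documented gap.
- Report a household-adjusted 95% CI for the primary rate, using either the protocol's cluster variance or a robust Poisson model with a log person-time offset, with limits on the log scale. Do the same for secondary rates where counts allow. Label adjusted limits approximate below about 15 cases, and give only the exact CI at zero cases.
- Keep the exact Poisson CI as supplementary, with its upper limit corrected to CINV(1 - alpha/2, 2*(n + 1)).
- If rho is reported, divide DE - 1 by mean subjects per household minus 1. If household sizes vary widely, use the size-weighted mean (sum of m squared over sum of m, where m is household size). For sizes 2 to 8 and rho 0.4 this gave (2.87 - 1)/(5.8 - 1) = 0.39, against 0.47 with the simple mean.
- State whether blocks or streets were sampled first. If they were, say that the household adjustment does not cover that level.
- Record the method in SAP section 8, and explain any remaining deviation in the final report.

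The cost is SAP wording and a few lines of code, since the household number is already in the eCRF (Protocol 6.5.2.1). Intervals will widen if cases cluster and hardly change if they do not.

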3.1. Discussion of study design

This prospective cohort study including children aged less than 18 years and adults aged up to 50 years is designed to support the selection and definition of clinical and laboratory endpoints for future dengue vaccine efficacy trials and to provide incidence data for sample size calculation. In addition, the study aims to train investigators and their teams on protocol specific processes and procedures, in preparation for the conduct of anticipated future vaccine efficacy studies. **(Amended 01 March 2017)**

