5.2.2. Additional Consideration

Additional case definition of AFI was added to the analysis. See Table 2 for details of ad-hoc case definitions. Incidence rate along with 95% exact confidence interval of AFI based on the ad-hoc case definition due to LCD will be calculated.

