5.3. Secondary objective

5.3.1. Analysis of secondary objective planned in the protocol

The incidence rate of first AFI due to LCD by serotype (DENV 1 – 4) and incidence rate of AFI due to non-LCD with 95% exact confidence interval will be calculated for overall and age group (could you please put here the age categories?).

Description of signs and symptoms of AFI due to LCD and due to non-LCD will include the percentage of AFI presenting each sign or symptom (any intensity and grade 3) during the 7-day period from the onset of fever (body temperature 38°C/100.4°F). The sign or symptom of suspected dengue infection is summarized in Table 1. Duration of signs and symptoms will also be described for LCD and non-LCD episodes. Analysis will be done overall and then separately by age group.

Table 1 Solicited symptoms of suspected dengue infection

Signs and symptoms
body temperature and route (minimum of two measurements)
headache / irritability
eye pain
myalgia (muscle pain)
arthralgia (joint pain)
abdominal pain
nausea
vomiting
rash
any bleeding (skin, mouth, anus)
loss of appetite
Fatigue/decrease in normal activity
reduced fluid intake

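### SAP 9.2.2 prints the exact Poisson upper limit with the 47.5th chi-square percentile instead of the 97.5th; programmed as written, the 95% interval covers about 50% at 10 to 60 cases

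*SAP*

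**What the plan says.** SAP 9.2.2 names its method plainly: "To estimate the confidence interval of the incidence rate, the exact Poisson confidence interval will be used". It prints the lower limit as the chi-square quantile at probability alpha/2 on 2n degrees of freedom, halved, divided by the person-years and scaled to 1000. It prints the upper limit as "CINV((1-\alpha)/2, 2*(n+1))/2/Ny*1000". It defines the first argument of CINV as the probability and the second as the degrees of freedom, and gives alpha as the type I error rate, "which will be 0.05 for calculating a 95% CI".

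The primary analysis in SAP 5.2.1 asks for a 95% exact interval and points here: "See section 9.2.1 and section 9.2.2 for details of incident rate and confidence interval calculation respectively". Two further sections ask for 95% exact intervals without citing 9.2.2:

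- SAP 5.2.2, for the ad-hoc case definition: "Incidence rate along with 95% exact confidence interval of AFI based on the ad-hoc case definition due to LCD will be calculated".
- SAP 5.3.1, for the DENV types and for non-LCD illness: "incidence rate of AFI due to non-LCD with 95% exact confidence interval will be calculated for overall and age group".

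Section 9.2.2 holds the only exact-interval formula for rates in the SAP. The tertiary rates in SAP 5.4.1 ask only for a 95% CI and do not cite 9.2.2, so they are left out of this point.

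Protocol 9.2, Table 17, lists exact Poisson 95% limits at 3300 person-years for ten case counts.

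**The concern.** The two printed limits do not belong to the same interval. The lower one leaves 2.5% in its tail, which fixes a two-sided, equal-tailed convention. With alpha = 0.05, the upper one is taken at the 47.5th percentile, close to the middle of the distribution. No reading of the printed expression gives a 95% interval.

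The study's primary aim is to estimate one incidence rate, so the interval around that rate is its main statement of precision. Protocol 3.1 says the study is meant, among other things, "to provide incidence data for sample size calculation" for future vaccine efficacy trials. A program that followed the text would report an interval with almost none of its upper half, labelled 95% exact. A reader planning a trial would take the rate as much better bounded from above than it is.

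**Working it through.** **Inputs.** alpha = 0.05 and both limit formulas: SAP 9.2.2. Person-years = 3300 and the ten case counts: protocol 9.2, Table 17. Table 17 is per 100 person-years; the SAP reports per 1000.

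**Formulas, in events; divide by person-years for a rate.**

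- Lower limit, as printed and correct: chi-square quantile at 0.025 on 2n df, divided by 2.
- Upper limit as printed: chi-square quantile at (1 - 0.05)/2 = 0.475 on 2(n+1) df, divided by 2.
- Exact upper limit: chi-square quantile at 1 - 0.05/2 = 0.975 on 2(n+1) df, divided by 2.

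**Step 1: reproduce the protocol's figures (per 100 person-years).**

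| Cases | Table 17, Poisson exact | Lower limit and 0.975 quantile | Upper limit with 0.475 |
|---|---|---|---|
| 10 | 0.15 to 0.56 | 0.15 to 0.56 | 0.32 |
| 20 | 0.37 to 0.94 | 0.37 to 0.94 | 0.62 |
| 30 | 0.61 to 1.30 | 0.61 to 1.30 | 0.92 |
| 40 | 0.87 to 1.65 | 0.87 to 1.65 | 1.22 |
| 50 | 1.12 to 2.00 | 1.12 to 2.00 | 1.52 |
| 60 | 1.39 to 2.34 | 1.39 to 2.34 | 1.82 |
| 4 | 0.03 to 0.31 | 0.03 to 0.31 | 0.14 |
| 8 | 0.10 to 0.48 | 0.10 to 0.48 | 0.26 |
| 12 | 0.19 to 0.64 | 0.19 to 0.64 | 0.38 |
| 16 | 0.28 to 0.79 | 0.28 to 0.79 | 0.50 |

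The 0.975 quantile matches all ten rows. The 0.475 quantile matches no upper limit.

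**Step 2: size of the error and coverage.** Limits are per 1000 person-years at 3300 person-years. Coverage is the sum of Poisson probabilities, at a mean equal to the case count, over all counts whose interval contains that mean. It assumes independent events, so no clustering.

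| Cases | Rate | Printed upper | Exact upper | Printed / exact | Coverage as printed |
|---|---|---|---|---|---|
| 10 | 3.03 | 3.17 | 5.57 | 0.57 | 52.8% |
| 20 | 6.06 | 6.18 | 9.36 | 0.66 | 50.8% |
| 30 | 9.09 | 9.19 | 12.98 | 0.71 | 50.2% |
| 40 | 12.12 | 12.20 | 16.51 | 0.74 | 50.1% |
| 50 | 15.15 | 15.22 | 19.98 | 0.76 | 49.5% |
| 60 | 18.18 | 18.24 | 23.40 | 0.78 | 49.8% |

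For example, at 40 cases the printed upper limit is 40.27 events and the exact one 54.47; 40.27/3300 × 1000 = 12.20 and 54.47/3300 × 1000 = 16.51. From 10 to 60 cases the printed limit is only 4.7% down to 0.3% above the estimate. At means 10, 20, 40 and 60 the true mean exceeds the printed upper limit with probability 45.8%, 47.0%, 47.9% and 48.3%; the nominal maximum is 2.5%. The true exact interval covers 95.3% to 97.5% at the six means.

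**Step 3: sparse counts, as may occur for a single DENV type.** At n = 0 there are 2 degrees of freedom and the limit is -ln(1 - p). The printed formula gives -ln(0.525) = 0.64 events and the exact one -ln(0.025) = 3.69. At n = 1 the limits are 1.60 and 5.57 events; at n = 4, 4.54 and 10.24. Coverage as printed is 61% at a mean of 1 and 55% at a mean of 4.

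**Step 4: large counts.** The documents give no expected number of non-LCD cases. If an outcome reached 113 or more first events, the printed upper limit would fall marginally below the estimate itself (0.42 events below at n = 300). The effect is small, but an upper limit under its own estimate confirms that the expression is wrong.

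**The case against.** The strongest objection concerns seriousness. The intended method is clear from the same section: it names the exact Poisson interval, says 95%, and gives a correct lower limit. A programmer using a standard routine would never type this expression, and one who did might notice an upper limit of 10.47 events for 10 cases. The documents do not show the program, all analyses are descriptive, and no success criterion depends on the limit. All of that is true, and it is why the claim is confined to the formula being programmed as written. It does not make the text right: this is the formula that the primary analysis cites, and nothing else in either document corrects it.

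Two qualifications stand.

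- Protocol 9.6 asks only for a 95% CI, and Table 17 is a planning table. The printed formula therefore conflicts with the SAP's own 95% label and with Table 17's Poisson exact column, not with an analysis method that the protocol prescribes.
- The coverage figures assume no clustering. SAP 9.2.2 is headed "The method for estimating the CIs for incidence rate not accounting for clustered data", while protocol 9.2 plans on a design effect of 2.6. Under that design effect a nominal 95% unclustered interval has a multiplier of about 1.96/√2.6 = 1.22, or roughly 78% coverage by the normal approximation. Correcting the bracket restores the named method; it does not by itself give 95% coverage in a clustered sample.

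A fault in reading the PDF cannot be wholly excluded. However, the brackets balance and the neighbouring lower-limit formula is intact. A look at the source SAP would settle it.

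**Conclusion.** The concern holds and should be fixed. As printed, the upper limit uses probability 0.475 where 0.975 is required. At 10 to 60 cases and 3300 person-years it lies 43% to 22% below the exact limit and almost on the point estimate, and coverage is about 50%. These sizes rest on the protocol's planning figure for person-years, on independent Poisson counts, and on the formula being programmed as written. The error directly affects the primary incidence rate through SAP 5.2.1. It also affects the ad-hoc, DENV-type, non-LCD and age-group rates to the extent that the exact intervals they call for are taken from 9.2.2.

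**What to change.** In SAP 9.2.2, write the upper limit as CINV(1-alpha/2, 2*(n+1))/2/Ny*1000. Before release, run the program on the ten case counts of protocol Table 17 at 3300 person-years and confirm that it returns the Poisson exact column, allowing for the change from per 100 to per 1000 person-years.

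As a small separate addition, state that the lower limit is 0 when n = 0, because the chi-square quantile on 0 degrees of freedom is undefined.

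The cost is a one-line SAP correction and one program check. If the program followed the printed text, the reported intervals become wider; if it already used 0.975, no result changes.

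Clustering still needs its own answer. For 40 cases, the design effect of 2.6 gives an upper limit of (40 + 1.96 × √(2.6 × 40))/3300 = 1.82 per 100 person-years, or 18.2 per 1000, against 16.51 for the corrected exact limit.
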